- m. X-rays of hands and feet will be performed for all subjects at Screening, Wk 24, Wk 56, Wk 104, Wk 152 and Wk 260/PD visits. All subjects who fail to attain at least 20% improvement in either or both TJC and SJC at Week 12 and Week 16 will have an x-ray examination at Week 16. An x-ray examination at Week 16 is not required for subjects with at least a 20% improvement in either or both TJC and SJC at Week 12 and Week 16. All subjects will receive x-rays of hands and feet if they discontinue from the study or from study drug at Week 12 or later and it has been at least 12 weeks from when x-rays were last obtained during Period 1 or at least 24 weeks during Period 2.
- n. Randomization is permitted prior to results of the central reading of hand and foot x-rays for eligibility if a subject has an elevated hs-CRP available from the central laboratory and all other criteria are met.
- o. For all women of childbearing potential, collect serum for pregnancy test at Screening and if any urine pregnancy test is positive at any time during the study. If the serum pregnancy test is positive the subject is considered a screen failure. If serum pregnancy test comes back borderline, a repeat test is necessary (pregnancy is an exclusion criterion). If still borderline ≥ 3 days later, this will be considered documentation of continued lack of a positive result and the subject can be enrolled into the study. Refer to Section 5.3.1.1 Study Procedures Pregnancy Test for additional details.

[figure not shown]
- p. For all female subjects of childbearing potential, collect urine for pregnancy test at Baseline and all subsequent visits. More frequent pregnancy tests will be performed throughout the study if required per local/country requirements. If urine pregnancy test (which is performed at the site) is negative, begin or continue dosing. If urine pregnancy test is positive, withhold dosing and perform a serum pregnancy test. Pregnant subjects must discontinue from study drug treatment. Refer to Section 5.3.1.1 Study Procedures Pregnancy Test for additional details.

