9.1.2 Handling of Missing Data and Intercurrent Events

Non-Responder Imputation (NRI) Approach

The NRI approach will handle data for binary endpoints as follows.

- Subjects who prematurely discontinue from study drug will be considered as non-responders for all subsequent visits after discontinuation.
- In addition, any subject with any missing value for the binary endpoints at a specific visit will be treated as non-responder for that visit.

NRI data handling will be used for the primary estimand (refer to Section 9.2.1) for the binary endpoints.

Mixed-Effects Model Repeated Measures (MMRM) Up to Week 24

The repeated measure analysis will be conducted using mixed models including observed data at all visits. For the MMRM analysis, data collected after premature discontinuation

of study drug will be excluded. The mixed model includes the categorical fixed effects of treatment, visit, treatment-by-visit interaction, the stratification factor current DMARD use (yes/no) and the continuous fixed covariates of baseline measurement. An unstructured variance covariance matrix will be used. The parameter estimations are based on the assumption of data being missing at random (MAR) and using the method of restrictive maximum likelihood (REML). MMRM will be used for the primary estimand of the non-radiographic continuous endpoints (refer to Section 9.2.3).

[figure not shown]
Linear Extrapolation for Radiographic Data

For radiographic data (i.e., SHS-based endpoints), linear extrapolation will be applied to subjects with missing data including those due to premature discontinuation of study drug or meeting the rescue criteria, where the missing x-ray at the time point of interest will be imputed assuming a linear relationship across visits. Linear extrapolation will be used to facilitate the primary estimand for radiographic endpoints (refer to Section 9.2.3). Linear extrapolation will not be provided for Week 104 analysis and future analyses.

As Observed (AO)

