To incorporate the uncertainty of a single imputation, the Multiple Imputation (MI) analysis will be conducted as a sensitivity analysis. The proposed MI model for the change from baseline in SHS score will be based on the linearity assumption for the subjects with missing data including those due to premature discontinuation of study drug or meeting the rescue criteria. More specifically, the regression method will be used where missing Week 24 observations will be imputed by regression upon all previous visits including baseline and Week 16, stratified by treatment group. The imputation model will also include baseline demographics and key baseline characteristics as appropriate. Analysis of covariance (ANCOVA) will be performed on each of the multiple imputed datasets. The results will be aggregated across the multiple imputed datasets using Rubin's method. The detailed SAS procedure are outlined in Appendix D.

The supplementary analysis will be performed using AO data handling with the same ANCOVA model. The corresponding estimand for the AO analysis is the difference in the mean change from baseline in SHS score at Week 24, regardless of premature discontinuation of study drug or use of rescue medication, comparing each upadacitinib dose group vs placebo. The analysis will be conducted for those who are randomized, received study drug and have the efficacy measurement at Week 24 visit.

The LS mean and 95% CI for each randomized treatment group and the LS mean treatment difference, the associated 95% CI and the p-value between each upadacitinib dose group and the combined placebo group will be provided.

In another sensitivity analysis, a random coefficient model will be applied, in which SHS measurements are used as the response variable, including measurements at Baseline and post-Baseline. The model is specified with a random intercept and a random slope on time, and includes treatment, current DMARD use (yes/no), and treatment-by-time

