                                          2' then output miparm1;
proc transpose data=miparm1 (keep= Shift1 Shift2 Probt)
out=wide miparm1;
by shift1;
id shift2;
var Probt;
run:
```

Note: The input dataset ALL includes all (# of shift1 parameters) * (# of shift2 parameters) * (# of imputations in MI) imputed datasets. TRTP denotes the treatment group and STRATA denotes the stratification factor used in analysis. CHG denotes the change from baseline value and BASELINE denotes the baseline value.

[figure not shown]
MI Analysis for Radiographic Continuous Endpoints

The MI analysis will impute missing data multiple times under appropriate random variation and thus generate multiple imputed "pseudo-complete" datasets. The imputation assumes of missing at random (MAR). ANCOVA will be performed on each of the multiple imputed datasets. The results will be aggregated across the multiple imputed datasets using Rubin's method. The SAS procedure PROC MI with the monotone

statement and REGRESSION method is used. Before applying PROC MI, MCMC is applied where necessary to augment data into monotone missing pattern. The SAS code example for PROC MI is as follows:

PROC MI DATA=DATA WIDE OUT=OUTMI NIMPUTE=1 SEED=12345;

[figure not shown]
```
Mcmc impute = monotone;
      VAR &COVCON base aval;
       By trtp;
RUN:
PROC MI DATA=DATA WIDE OUT=OUTMI NIMPUTE=20 SEED=12345;
      CLASS &COVCAT;
     MONOTONE;
      VAR &COVCON &COVCAT base aval;
       By trtp;
RUN:
       The input dataset is in wide format. TRTP denotes the treatment group. &COVCON denotes baseline
Note:
       continuous covariates including baseline age, baseline BMI, duration of PsA diagnosis and baseline value of
       the endpoint of interest. &COVCAT denotes categorical covariates including current use of non-biologic
       DMARD, gender, race and regions. WEEK 16, WEEK 24 denote the observed values at each visit.
PROC MIXED DATA=ALL;
    ODS OUTPUT LSMEANS=MIXEDLSMEANS DIFFS=DIFF;
    BY IMPUTATION ;
    CLASS TRTP STRATA;
    MODEL CHG = BASELINE TRTP STRATA / SOLUTION;
    LSMEANS TRTP / CL PDIFF DIFF;
RUN:
DATA DIFF1;
    SET DIFF;
    COMPARISON= TRTP||' VS '||LEFT( TRTP);
RUN;
PROC SORT DATA=DIFF1; BY COMPARISON IMPUTATION ; RUN;
PROC MIANALYZE DATA=MIXEDLSMEANS1;
ODS OUTPUT PARAMETERESTIMATES=GROUP OUTPUT;
BY TRTP;
MODELEFFECTS ESTIMATE;
```

```
STDERR STDERR;
RUN;

PROC MIANALYZE DATA=DIFF1;
    ODS OUTPUT PARAMETERESTIMATES=GROUP_OUTPUT;
    BY comparison;
    MODELEFFECTS ESTIMATE;

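### The Appendix D code for the SHS multiple-imputation sensitivity analysis leaves out Week 16 and does not chain its two steps, and the SAP does not say whether post-rescue Week 24 films enter it

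*SAP*

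**What the plan says.** SAP Section 9.2.3 (Radiographic Endpoints) introduces the analysis as a way to carry the uncertainty that a single imputation hides. It bases the model on linearity and specifies that "missing Week 24 observations will be imputed by regression upon all previous visits including baseline and Week 16, stratified by treatment group". It sends the reader to Appendix D for the detailed SAS procedure.

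Appendix D describes two stages: "Before applying PROC MI, MCMC is applied where necessary to augment data into monotone missing pattern", followed by monotone regression. In the code, the first call is "PROC MI DATA=DATA WIDE OUT=OUTMI NIMPUTE=1 SEED=12345" and the second is "PROC MI DATA=DATA WIDE OUT=OUTMI NIMPUTE=20 SEED=12345". The variable list of the second call is "VAR &COVCON &COVCAT base aval"; the first has the same list without the categorical covariates. A note under the code defines Week 16 and Week 24 variables, but no statement uses them.

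On which values count as missing, SAP Section 9.1.2 applies linear extrapolation to missing radiographic data, including data missing because of "premature discontinuation of study drug or meeting the rescue criteria". Section 9.2.3 uses the same criterion for the multiple imputation.

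On which films exist, Protocol Appendix C, footnote m, schedules hand and foot films for all subjects at Week 24. It schedules a Week 16 film only for subjects who miss the 20% joint-count criterion, and adds: "An x-ray examination at Week 16 is not required for subjects with at least a 20% improvement in either or both TJC and SJC".

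**The concern.** This analysis is meant to test the single-imputation step behind the structural-progression result. Subjects who meet the rescue criteria are likely to be the ones progressing, and the Week 16 film is the only post-baseline structural information collected on them before background therapy may change. If the imputation model leaves that film out, rescued subjects are given values typical of non-rescued subjects with the same baseline in their arm. A gap between this analysis and the primary one would then reflect discarded films rather than imputation uncertainty, and a reader could misjudge how robust the primary result is.

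The second worry is that correcting the code may not be enough. If the subjects with a Week 16 film are the same subjects whose Week 24 value is set aside, nothing in the data says how Week 24 depends on Week 16.

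**Working it through.** **1. The plan's own figure for this endpoint.** SAP Section 4.3 gives about 90% power at a standardized effect of 0.26, two-sided alpha 0.025 and 10% dropout. With 410 per group, n = 410 × 0.9 = 369. Power = Φ(0.26 × √(369/2) − 2.241) = Φ(3.532 − 2.241) = Φ(1.290) = 90.2%. The figure reproduces, and nothing below changes it.

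**2. Text against code.**

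| Item | SAP text | Appendix D code |
|---|---|---|
| Predictors of Week 24 | Baseline, Week 16, baseline characteristics | Baseline covariates and baseline SHS; one outcome variable; no Week 16 |
| Input to second call | Output of the MCMC step | The original wide dataset again |
| OUTMI after both calls | Monotone data, then imputed | Second call's output only; first call's result lost |
| Time trend | Linearity (Section 9.2.3) | None imposed; Appendix D states missing at random |

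**3. Does skipping the MCMC step matter?** Little, with the lists as written: apart from baseline covariates only one variable can be missing, so the pattern is already close to monotone. Once Week 16 is added, subjects who have Week 24 but no Week 16 break the monotone pattern, and the step is needed. Chaining the calls as they stand would still be incomplete, because NIMPUTE=1 followed by NIMPUTE=20 carries no uncertainty from the first step.

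**4. Is Week 24 on Week 16 estimable?** There are two readings.

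- *Observed post-rescue Week 24 films enter.* Rescued subjects who stay in the study have both films and the regression has data. Those subjects then need no imputation, which conflicts with the Section 9.2.3 estimand, where their Week 24 value is predicted from the baseline and Week 16 windows.
- *Those films are set to missing.* Scheduled Week 16 films belong to subjects with no usable Week 24 value, and other subjects generally have no Week 16 film.

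The second reading was checked by simulating one arm of 410. All inputs are assumed: rescue probability 30% (117 rescued), baseline mean 13 (SD 5), mean Week 24 change 0.5 if rescued and 0.1 if not (SD 1), linear progression, and error SD 0.3 at each film. No subject has both values. A trivariate normal model was fitted by EM from five starting partial correlations between Week 16 and Week 24 given baseline:

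| Start | End | Log-likelihood |
|---|---|---|
| −0.9 | −0.90 | −1038.6028 |
| −0.5 | −0.50 | −1038.6028 |
| 0 | 0.02 | −1038.6028 |
| 0.5 | 0.52 | −1038.6028 |
| 0.9 | 0.91 | −1038.6028 |

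The fit stays about where it starts at an identical likelihood, so the association is not identified. The mean imputed change for rescued subjects was 0.08 from every start. The code as written also gives 0.08, equal to the non-rescued mean of 0.08. Linear extrapolation, (24/16) × the Week 16 change, gives 0.55; the simulated truth is 0.50. On this reading, adding Week 16 to the list does not by itself bring the Week 16 information into the arm mean.

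**5. Illustrative size.** Let p_P and p_U be the rescued fractions on placebo and upadacitinib, and c the rescued Week 24 change. Assume non-rescued changes of 0.1 on placebo and 0.0 on upadacitinib.

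- Linear extrapolation: difference = (1 − p_P) × 0.1 + p_P × c − p_U × c.
- Code as written: rescued subjects take their arm's non-rescued mean, so difference = 0.1 − 0.0 = 0.10.

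Lowest case (p_P 0.20, p_U 0.10, c 0.3): 0.08 + 0.06 − 0.03 = 0.11. Highest case (p_P 0.40, p_U 0.15, c 1.0): 0.06 + 0.40 − 0.15 = 0.31. None of these inputs is in the documents.

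**The case against.** The code is labelled an example, and the governing sentence in Section 9.2.3 is correct, so a programmer could be expected to follow the text. This stands as a limit: the executed program is not visible, and the documents do not show that it had the defect. It does not remove the point, because Section 9.2.3 refers to Appendix D for the procedure. The omission is also hard to read as shorthand, since the tipping-point code in the same appendix lists its visits one by one.

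A reader might infer that hardly any subject has both films. The documents do not support that. Week 24 films are scheduled for everyone, rescued subjects included, and the as-observed analysis uses them. A Week 16 film in a responder is not required, but it is not ruled out, and the Week 16 window in Table 6 runs from Day 2 to Day 141. The overlap is small only among values this imputation may use, and only if post-rescue and post-discontinuation Week 24 values are set aside. That is the likelier reading of Sections 9.1.2 and 9.2.3, but neither says so outright, and the code note speaks of observed values at each visit.

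The missing Week 16 term and the skipped MCMC step should not be counted as two present failures; the second has little effect until the first is corrected.

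Finally, SAP Section 11.1 says the primary efficacy analysis was completed under SAP version 3.0 and that this version governs only later long-term reporting. A correction would therefore not be prospective. Version 4.0 still carries the text, so the record needs checking.

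**Conclusion.** The code is wrong as written: it does not perform the analysis in Section 9.2.3, and followed literally it ignores the Week 16 film of every subject whose Week 24 SHS is imputed. That rests on the SAP text alone. The identification problem is conditional on post-rescue and post-discontinuation Week 24 values being treated as missing. It was shown with an EM fit on simulated data, not by running PROC MI, so nothing is claimed about what the software's default prior would supply. The number of subjects affected is unknown, and the differences of 0.11 to 0.31 against 0.10 illustrate direction only.

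A reader might infer that the ranked SHS test is compromised. It is not. That test uses ANCOVA with linear extrapolation, which draws on the Week 16 window, and an as-observed analysis and a random-coefficient model are planned beside it. What is at stake is one sensitivity analysis and the reassurance drawn from it.

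**What to change.** 1. State whether observed Week 24 films after rescue and after discontinuation enter the multiple imputation.
2. Put baseline SHS (once; it now appears both among the continuous covariates and as a separate variable), Week 16 and Week 24 in the variable lists. Create 20 monotone datasets in the first step, then run the second step on that output by imputation number with NIMPUTE=1.
3. If post-rescue Week 24 values are excluded, do not rely on an unconstrained regression of Week 24 on Week 16. Impose the stated linearity explicitly. One option is to draw the imputations from a random-slope model of the kind Section 9.2.3 already plans, with a stated fallback for non-convergence. Item 1 must be settled for that model too, because Section 9.2.3 does not say whether post-rescue films enter it.
4. Check the program that was run. If it followed the example code, rerun this sensitivity analysis or correct the record.

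The cost is a few lines of SAP text and reprogramming one sensitivity analysis. No new data are needed, and the sample size and primary SHS analysis do not change.

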Appendix F. Statistical Analysis to Account for the Impact of COVID-19 Pandemic

This section presents the changes in statistical analysis to handle the missing data due to COVID-19 and the additional data collected related to COVID-19. The Week 24 primary database lock was completed in Jan 2020. The analyses specified in this section only applies to the long-term database lock.

Patient Disposition

Reasons for premature discontinuation of study drug/study will be updated to add two additional reasons related to COVID-19.

[figure not shown]
- COVID-19 Infection
- COVID-19 Logistical restrictions

The number and percentage of subjects who prematurely discontinued from study drug/study due to COVID-19 infection or COVID-19 logistical restrictions will be summarized by randomized treatment group.

Summary of COVID-19 Impacted Visits

Types of missing visits related to COVID-19 will be collected for the protocol prespecified visits. For each visit, the number and percentage of subjects impacted by COVID-19 will be summarized by the types of visit for each randomized treatment group as well as overall:

- In person, partial assessments done
- Virtual visit
- Missed visit

Efficacy Analyses

With respect to COVID-19 pandemic, it would be reasonable to assume that missed visits and missing data due to self-quarantine or local government restrictions on travel or limitations on healthcare resources will impact subjects across treatment arms in a similar fashion and adopt the Missing at Random (MAR) assumption for missing data handling.

As described in Section 9.3, longitudinal analysis models MMRM and GLMM, as well as NRI analysis for binary variables will be used for long term efficacy analysis for the treatment sequences, and will be maintained for long term efficacy analysis in the presence of missing data due to COVID-19.

Additionally, treatment comparisons between each upadacitinib dose versus adalimumab will be made for non-radiographic efficacy endpoints for the originally randomized upadacitinib groups and adalimumab group.

For radiographic related endpoints, the analysis will be based on linear extrapolation imputation (Week 24 and Week 56 analysis) and AO data. MMRM will be used for continuous radiographic endpoints for Week 104 and future analysis.

Safety Analyses

COVID-19 related AEs occurring on or after February 1, 2020 and COVID-19 related deaths occurring on or after February 1, 2020 will be collected.

Listings of subjects with AEs related to COVID-19 infection will be provided.

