Vital sign determinations of systolic and diastolic blood pressure, pulse rate (counted for at least 30 seconds after 5 minutes in sitting position), respiratory rate, body weight, and body temperature will be obtained at the designated study visits in Appendix C. Vital signs should be performed before blood draws and prior to receipt of study drug. Height will be measured at the Screening Visit only (with shoes off). All measurements will be recorded in metric units where applicable.

[figure not shown]
Due to a state of emergency or pandemic situation, subject visits may be conducted via phone or video conference. In these situations, vital signs and weight may be performed by the subject or caregiver as needed.

Physical Exam

A complete physical examination will be performed at the designated study visits as specified in Appendix C. The physical examination at the Baseline Visit will serve as the baseline physical examination for the entire study. Physical examination abnormalities noted by the Investigator at the Baseline Visit prior to the first dose of study drug should be recorded in the subject's medical history. Abnormalities noted after the Baseline Visit and first dose of study drug should be evaluated and documented by the Investigator as to whether or not these are AEs. All findings whether related to an AE or part of each subject's medical history should be captured on the appropriate eCRF page.

A symptom-directed physical examination will be performed when necessary.

Due to a state of emergency or pandemic situation, subject visits may be conducted via phone or video conference. In these situations, if a visit by phone or video conference occurs at one of the designated study visits specified for complete physical examination, the complete physical examination will be performed at the next feasible visit.

12-Lead Electrocardiogram (ECG)

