9.1.1 Efficacy Analysis at Different Phases of the Study

[figure not shown]
Efficacy Analysis by Week 24

Standard efficacy analysis by randomized treatment groups (upadacitinib 15 mg QD, upadacitinib 30 mg QD, adalimumab 40 mg EOW and the combined placebo groups) will be performed on efficacy data up to Week 24. No protocol-defined treatment switching will occur prior to the time point. Formal statistical inference will be generated, and results from this set of analysis will be used as the key efficacy findings of this study.

Long-Term Efficacy Analysis

Long-term efficacy analysis will be performed on As Observed data (defined in Section 9.1.2) by randomized treatment group sequence as described below:

- 1. Placebo → Upadacitinib 15 mg QD
- 2. Placebo → Upadacitinib 30 mg QD
- 3. Upadacitinib 15 mg QD
- 4. Upadacitinib 30 mg QD
- 5. Adalimumab 40 mg EOW

Descriptive statistics and 95% confidence intervals will be provided for all treatment sequences. In addition, comparisons between each upadacitinib dose and adalimumab (treatment sequences 3, 4, and 5) will be provided up to Week 56. Treatment comparisons may also be provided after Week 56 as appropriate.

For long term efficacy analysis, subjects will continue to be summarized under the treatment sequences as described above, regardless of dose switch from upadacitinib 30 mg QD to upadacitinib 15 mg QD – i.e., for treatment sequences 2 and 4, data collected after dose switch will continue to be summarized under the same treatment sequences. The visit at which dose switch occurs could be different for each subject. The first and last visits at which dose switch occurs will be noted in the summary. In addition, sensitivity analyses will be performed where the subjects who switched from upadacitinib 30 mg QD to 15 mg QD will be censored at the time of dose switch, and efficacy values before and post switch will be summarized separately.

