9.4 Efficacy Variables Definitions and Conventions

9.4.1 ACR Criteria

ACR criteria are a commonly used standard criteria set mentioned in the FDA industry guidance to evaluate the effectiveness of investigational drug in reduction of disease activity. It is a composite measurement calculated based on the improvement over a set of core measurements.

ACR20 is defined as at least 20% improvement (compared to baseline values) in tender and swollen joint counts and at least 20% improvement in 3 of the remaining 5 core set measures (subject assessment of pain, subject global assessment of disease activity, physician global assessment of disease activity, subject assessment of physical function and acute phase reactant hsCRP).

ACR50 and ACR70 are similarly defined with at least 50% and 70% improvement, respectively.

A subject will be classified as an ACR20 (ACR50, ACR70) responder, if the following conditions are met:

- 1. $\geq 20\%$ (50%, 70%) improvement from baseline in tender joint count (TJC68) and
- 2. $\geq 20\%$ (50%, 70%) improvement from baseline in swollen joint count (SJC66) and
- 3. $\geq 20\%$ (50%, 70%) improvement from baseline in at least 3 of the following 5:
 - patient's assessment of pain
 - patient's global assessment of disease activity (PtGA)
 - physician's global assessment of disease activity (PGA)

- patient's self-assessment of physical function (i.e., measured by Health Assessment Questionnaire HAQ-DI score)
- Acute-phase reactant value CRP

Seven components are included in the ACR response criteria. Missing values for a component can occur due to data collection issues for a particular form, a missed visit or dropout from the study. Depending on the pattern of the missing components, ACR responses may be or may not be determined for a visit date using (partially) observed values only. In the case when ACR responses cannot be determined for any visit date within a visit window, partially observed data from different visit dates within the same visit window can be combined to determine ACR responses for the visit window.

To maximize the utilization of observed information at certain visits and be scientifically as robust as possible, the principle to calculate ACR response is to minimize imputation whenever possible. "As Observed" ACR response will be calculated first based on a derived visit window instead of the nominal visit identifier (e.g., Week 6 visit) collected from the CRF.

To calculate "as observed" ACR responses:

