Identify the observed component 20% improvement indicator (0/1/missing), 1 means achieving \geq 20% improvement from baseline and 0 means < 20% improvement from baseline.

ACR20 = 0 if TJC indicator = 0 OR SJC indicator = 0 OR at least 3 out of 5 components improvement indicators = 0;

ACR20 = 1 if TJC indicator = 1 AND SJC indicator = 1 AND at least 3 out of 5 components improvement indicators = 1.

For all other cases, "as observed" ACR20 = missing since ACR20 cannot be determined.

The following table illustrates examples for as-observed ACR calculations.

Example	TJC 68	SJC 66	Component 1	Component 2	Component 3	Component 4	Component 5	ACR20- Response?
A	1	1	1	1	1			Yes
В	1	0	1	1	1	1	1	No
C	•	0						No
D	1		1	1	1	1	1	
E	1	1	0	0	0	1	1	No
F	•		0	0	0			No
G	1	1	1	1	0	0		

Legend: 1 = 20% improved compared to baseline; 0 = 20% improved compared to baseline; "." missing

Derived visit windowing Rule for ACR Response Calculation:

To identify the component value in a visit window:

ACR component values will first be determined at each date within a visit window.

ACR component values at each date will be combined to determine the "as observed" ACR composite score at each date in each window.

After this calculation, if multiple non-missing ACR composite scores are available within a given visit window, the non-missing ACR composite score closest to the target day will be used. If two composite scores have the same distance from the target day, the later one will be used. The corresponding date will be used as the "observed" ACR response date in the derived efficacy dataset.

If a non-missing ACR composite score is not available for any day within a given visit window, the windowed component values for that visit will be used to calculate the ACR composite score for that visit window (component value windowing follow the same rules as in steps described above). Date of TJC will be used as the "observed" ACR date in the derived efficacy dataset.

The following rules are applied for the NRI imputation for the ACR responses.

Non-Responder Imputation (NRI):

- **Step 1:** all missing components will be imputed using LOCF, and then the ACR composite score can be calculated
- Step 2: if the ACR composite score cannot be determined by step 1, the ACR composite score will be imputed as 0. In addition, subjects who prematurely discontinue from the study drug will be considered as non-responders (ACR = 0) for all subsequent visits after the discontinuation date.

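### In the supplementary long-term NRI analysis, a COVID-19 gap in an examination-based, non-ACR binary endpoint counts as non-response, although Appendix F assumes such gaps are missing at random

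*SAP*

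**What the plan says.** **Assumption.** SAP Appendix F reasons that visits lost to quarantine, travel restrictions or stretched healthcare affect the arms alike. It considers it reasonable to "adopt the Missing at Random (MAR) assumption for missing data handling".

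**Methods kept.** The next paragraph states that "longitudinal analysis models MMRM and GLMM, as well as NRI analysis for binary variables will be used for long term efficacy analysis" of the treatment sequences, "and will be maintained for long term efficacy analysis in the presence of missing data due to COVID-19".

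**NRI rule.** SAP Section 9.1.2 makes subjects non-responders after they stop study drug, and adds that "any subject with any missing value for the binary endpoints at a specific visit will be treated as non-responder for that visit". The reason for the gap plays no part.

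**ACR exception.** SAP Section 9.4.1 has its own NRI steps for ACR. First, "all missing components will be imputed using LOCF, and then the ACR composite score can be calculated"; only a response that is still undetermined is set to failure. In addition, "partially observed data from different visit dates within the same visit window can be combined to determine ACR responses for the visit window". MDA (9.4.12) and PsARC (9.4.18) have the same in-window combination. Neither they nor sIGA, PASI, dactylitis and enthesitis (9.4.10, 9.4.11, 9.4.14, 9.4.15) have a carry-forward step.

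**Place of NRI.** SAP Section 9.1.1 says: "Long-term efficacy analysis will be performed on As Observed data". Section 9.3 adds NRI, GLMM, or both, for non-radiographic binary endpoints and does not say which leads.

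**Remote visits.** Protocol Section 5.3.1.1 provides that in a pandemic "subject visits may be conducted via phone or video conference", and that patient-reported outcomes (PROs) may be collected on paper or by telephone.

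**Scope.** Appendix F applies only to the long-term database lock. Section 11.1 limits SAP version 4.0 to future long-term reporting.

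**The concern.** NRI is not a MAR method. It treats a gap as if failure had been observed. That is defensible when a gap is likely to reflect the drug, as after discontinuation. It conflicts with the SAP's own statement that pandemic gaps arise from circumstances that affect the arms alike.

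Take a subject in stable MDA who stays on study drug and is seen only by telephone in one window. That subject is a responder before the visit, an NRI failure at it, and a responder after it. The NRI curve then dips with the calendar and not with the drug. At stake is the reading of the supplementary NRI curves for Period 2, and of any upadacitinib–adalimumab difference reported on the NRI scale.

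**Working it through.** The plan states no figure on this point, so there is nothing to reproduce. The check has two parts: which endpoints reach the failure rule, and how large the effect is under stated assumptions.

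**1. Which endpoints reach the rule**

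Protocol Section 5.3.1.1 describes joint counts by pressure, LDI by dactylometer and squeeze, and LEI by tenderness on examination. It gives no remote procedure for any of them.

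- MDA needs 5 of 7 criteria. Pain, patient global assessment and HAQ-DI are the only three that are patient-reported. A telephone visit is therefore 5 − 3 = 2 criteria short of establishing response.
- PsARC response requires improvement in a joint count.
- PASI is not scored if one item is missing, and sIGA is the investigator's rating of lesions. The documents do not say whether a site could rate skin by video.
- Enthesitis and dactylitis resolution rest wholly on the examination.

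If no other assessment falls in the window, response cannot be established and Section 9.1.2 scores non-response.

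**2. Size under the plain rule**

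Inputs, all assumed:

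- p is the share of subjects who truly respond while on study drug.
- m is the share still undetermined after windowing because of a COVID-19-impacted visit.
- Being undetermined is independent of response. Without this, m should be read as the share among true responders. That matters for MDA, because a telephone visit can show three criteria unmet but can never show five met.

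Expected NRI rate = p(1 − m), so the shortfall is p × m.

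| p | m = 5% | m = 10% | m = 20% |
|---|---|---|---|
| 40% | 38% (−2 points) | 36% (−4) | 32% (−8) |
| 60% | 57% (−3) | 54% (−6) | 48% (−12) |
| 70% | 66.5% (−3.5) | 63% (−7) | 56% (−14) |

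**3. Differences between arms**

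With equal m, p₁(1 − m) − p₂(1 − m) = (p₁ − p₂)(1 − m). An assumed 5-point difference (70% against 65%) becomes 4.75, 4.5 and 4.0 points at m = 5%, 10% and 20%.

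**4. ACR20/50/70**

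With carry-forward first, the rate is about (1 − m)p + m × p_prev, where p_prev is the response rate at the preceding visit. It equals p when response is stable. This was simulated with 400,000 subjects, a stable p, and a 0.85 or 0.95 chance that a responder stays one. Last-visit response stood in for component carry-forward. At p = 60% the NRI rate was 0.600 for every m, against 0.599 to 0.600 as observed. There was no systematic shortfall.

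**5. As Observed and GLMM**

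Under Section 9.1.2 a subject without an evaluation is left out of the As Observed analysis at that visit, and the long-term GLMM uses the same data. Neither converts a gap to failure.

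**The case against.** The strongest reply is that NRI is a deliberately conservative supplement. The main long-term handling is As Observed, GLMM fits the MAR statement, and showing a conservative analysis beside them is no contradiction. COVID-19-impacted visits will be tabulated by visit and type, so a reader can see where a dip coincides with them. Visit windows also help: in SAP Table 4 the Week 56 window runs from day 324 to day 435, Period 2 windows are defined similarly, and procedures may be done at unscheduled visits. A late in-person assessment can therefore supply the value.

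Much of this stands, and it limits how far the point reaches. It does not remove it. The As Observed and GLMM analyses use data regardless of study drug discontinuation, so they answer a different question from NRI, which counts response only while on drug. No planned long-term analysis keeps that target and also treats pandemic gaps as the SAP says they should be treated. Section 9.3 also allows NRI to be the only added binary analysis. The visit table shows where the problem may lie but does not correct the rates.

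Two stronger readings are tempting, and the documents do not support them:

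- A reader might infer that every virtual or missed visit becomes a treatment failure. ACR has carry-forward. Endpoints based only on PROs, such as HAQ-DI improvement and BASDAI 50, can be captured remotely. Partial data within a window can be combined for ACR, MDA and PsARC.
- A reader might equate m with the share of COVID-19-impacted visits. The relevant m is the share still undetermined, which cannot be larger and may be much smaller.

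**Conclusion.** The point holds for the supplementary long-term NRI analysis of MDA, PsARC, PASI, sIGA, and enthesitis and dactylitis resolution. For these, Appendix F's MAR assumption and the unmodified rule in Section 9.1.2 disagree. NRI rates are too low by about p × m: 3, 6 or 12 points at an assumed p of 60% and m of 5%, 10% or 20%. NRI differences between arms shrink by the factor (1 − m) if m is equal across arms. These sizes rest on assumed values of p and m and on independence of the gap from response. The documents give no rate of COVID-19 missingness.

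It would be wrong to conclude that long-term response is understated in general. The As Observed, GLMM and MMRM analyses and the radiographic endpoints are not subject to this rule. The primary and ranked results are also untouched, because Appendix F dates the Week 24 lock to January 2020 and applies only to later data. Comparisons with adalimumab after Week 56 are optional, and Section 9.3 describes them alongside the As Observed results, so the shrinkage matters only if NRI differences are reported.

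The change is worth making because it is cheap and follows from the SAP's own assumption. No confirmatory conclusion depends on it.

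**What to change.** In SAP Appendix F and Section 9.3, for Week 104 and later:

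- Multiply impute, under MAR and within treatment sequence, only those binary values that are still undetermined after windowing because of a visit flagged as missed, virtual or partial for COVID-19.
- Keep non-response for all other missing values and for all visits after study drug discontinuation.
- Retain unmodified NRI as a sensitivity analysis.
- State in Section 9.3 whether NRI, GLMM or both will be reported, and which leads.

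The cost is SAP wording and one imputation step. Appendix F already plans to collect the visit types, and Protocol Section 10.2 already calls for supplemental case report forms for COVID-19-related missing, incomplete or virtual visits. The small downside is that the results then depend on an imputation model; the retained NRI table shows how much.
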